8.2. Adverse Events

The planned summaries for AEs are provided in [Table JAHW.8.2](#) and are described more fully in compound-level safety standards and in the AE-related PHUSE white paper (Analysis and Displays Associated with Adverse Events: Focus on Adverse Events in Phase 2-4 Clinical Trials and Integrated Summary Document [PHUSE resources pageWWW]).

Table JAHW.8.2. Summary Tables Related to Adverse Events

Analysis	Population or Analysis Set ^a
An overview table, with the number and percentage of subjects who experienced a TEAE, SAE, death, discontinued from study treatment due to an AE	A, L
The number and percentage of subjects with TEAEs using MedDRA Preferred Term nested within System Organ Class	A, L
The number and percentage of subjects with TEAEs using MedDRA Preferred Term (without regard to System Organ Class)	A, L
The number and percentage of subjects with TEAEs by maximum severity using MedDRA Preferred Term	A, L
The number and percentage of subjects with TEAEs using MedDRA Preferred Term for the common TEAEs (occurred in $\geq 1\%$ of treated subjects before rounding of the percentage)	A, L
The number and percentage of subjects who experienced a SAE (including deaths and SAEs temporally associated or preceding deaths) during the treatment period using MedDRA Preferred Term nested within System Organ Class	A, L
A listing of SAEs	Enrolled
The number and percentage of subjects who permanently discontinued from study treatment due to an adverse event (including adverse events that led to death) during the treatment period using MedDRA Preferred Term nested within System Organ Class	A, L

Abbreviations: AE = Adverse Event; MedDRA = Medical Dictionary for Regulatory Activities; SAE = Serious Adverse Event; TEAE = Treatment Emergent Adverse Event.

^a Analysis Sets are abbreviated as follows: A = Part A safety population, L = Long-term period.

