
 To evaluate the safety of baricitinib in children with JIA-U or ANA-positive uveitis 	
 Adverse events including serious adverse events. Permanent discontinuation of investigational product due to AE. Temporary interruption of investigational product.

Abbreviations: AE = adverse event; LogMAR = logarithm of the minimum angle of resolution;

PediACR = Pediatric American College of Rheumatology; SUN = Standardization of Uveitis Nomenclature.

a Response is defined according to the SUN criteria as a 2-step decrease in the level of inflammation (anterior chamber cells) or decrease to 0 through Week 24 in the eye most severely affected at baseline.

Summary of Study Design

Study I4V-MC-JAHW (JAHW) is a multicenter, open-label, active-controlled Phase 3 study in patients with active JIA-U or chronic ANA-positive uveitis without systemic features despite prior treatment with adequate doses of topical steroid therapy and MTX.

Treatment Arms and Duration

The study consists of 2 arms. Patients in the baricitinib arm will receive oral baricitinib at least QD at a fixed dose by age group. Patients in the adalimumab (active control) arm will receive adalimumab as a subcutaneous injection every 2 weeks. The dose will be based on body weight (adalimumab Summary of Product Characteristics [SmPC]).

Study JAHW will be conducted in 2 parts:

- Treatment Period Part A: 24 weeks
- Treatment Period Part B: 260 weeks.

Patients who complete Part A may be eligible to continue to Part B, the open-label extension (OLE) period of the study. Patients on adalimumab will be discontinued after Week 24. Patients who do not continue in the OLE will have a follow-up visit (Visit 801) approximately 28 days after the last dose of the investigational product.

Study Population

This study includes patients from 2 years to less than 18 years old with active JIA-U or chronic ANA-positive uveitis without systemic features despite prior treatment with adequate doses of topical steroid therapy and MTX.

Number of Patients

- Baricitinib arm: At least 20 patients (MTX-IR and/or bDMARD-IR) evaluable for primary endpoint.
- Adalimumab arm: At least 4 patients evaluable for the primary endpoint.

Statistical Analysis

A Bayesian analysis will determine if the study should be considered a positive study or a negative study. The study will be considered positive if the posterior probability is at least 80%

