4.2. Secondary Objectives

The secondary objectives of Study JAHW are grouped according to 2 periods defined in the study design:

Treatment Period Part A: 24 weeks

Treatment Period Part B: 260 weeks.

Baricitinib patients who complete Part A may continue to Part B, the open-label extension (OLE) period of Study JAHW. Patients on adalimumab will be discontinued after Week 24. Patients who do not continue in the OLE will have a follow-up visit (Visit 801) approximately 28 days after the last dose of the investigational product.

In particular, for Study JAHW, the secondary estimand is defined by

Population of interest: the population of interest for Part A of Study JAHW is patients who participate in Study JAHW Part A. The population of interest for Part B is patients who stay in Study JAHW Part B. Study JAHW patients are patients from 2 years to <18 years old with active JIA-U or chronic anterior ANA-positive uveitis. Analysis populations are defined in Section 6.1.1.

Variable (or endpoint) of evaluation: primary and secondary endpoints/variables are listed in [Table JAHW.4.1](#) and [Table JAHW.4.2](#). A full list of endpoints and variables is given in [Table JAHW.7.1](#) and [Table JAHW.7.2](#).

Population-level summary: the summary measure for binary variables will be proportion and the summary measure for continuous variables will be the average.

Intercurrent event(s) strategy: in Study JAHW Part A, for efficacy and health outcomes-related endpoints, the analysis population will be based on patients who have had the chance to complete the visits. In the estimand framework, for binary variables other than the primary outcome variable, the composite estimand strategy will be applied; nonresponder imputation will be applied to variables to support this strategy. The while-on-treatment strategy will be used for continuous variables, and last observation carried forward (LOCF) imputation will be used to support this strategy. For Part B, the analysis population will be based on completers for the specific analysis visit, and this method is referred as the as-observed analysis. The details of the imputation methods for the estimand and intercurrent events are described in Section 6.3. Statistical methods corresponding to each of the efficacy and health outcomes variables are summarized in [Table JAHW.7.1](#), [Table JAHW.7.3](#), [Table JAHW.7.3](#), and [Table JAHW.7.4](#).

The secondary objectives of Study JAHW are described in [Table JAHW.4.2](#).

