5.1. Summary of Study Design

Study JAHW is a multicenter, open-label, active-controlled Phase 3 study in patients with active JIA-U or chronic ANA-positive uveitis without systemic features, despite prior treatment with topical steroid therapy and methotrexate (MTX). Study JAHW will be conducted in 2 parts. Part A will include the screening period and treatment period (open-label treatment) with baricitinib and adalimumab up to Week 24. Part B (the OLE) will provide treatment for up to 5 years after Part A.

In the original Study JAHW design (Figure JAHW 5.1), patients who received baricitinib during Part A continued to receive baricitinib during Part B. Patients who received adalimumab during Part A continued to receive adalimumab for an additional 96 weeks and were then switched to baricitinib for the remaining 164 weeks of Part B.

Since then, Protocol JAHW and the study design have been modified (Figure JAHW 5.2). Patients currently assigned to baricitinib who have completed the primary endpoint as a responder will continue receiving baricitinib until the end of Study JAHW, or discontinuation from the study. The investigator may consult the study team for guidance on study continuation in the event the patient is a nonresponder at the primary endpoint, but demonstrates clinically meaningful benefit from baricitinib. Patients on adalimumab will discontinue Study JAHW after Week 24.

Figure JAHW 5.1 illustrates the study design from the previous amendment (d).

[figure not shown]

Abbreviations: bDMARD = biologic disease-modifying antirheumatic drug; IR = inadequate response or intolerance to; MTX = methotrexate; n = number of patients; OLE = open-label extension.

^a Patients \geq 6 to $<$ 12 years old assigned to baricitinib have the option of receiving the oral suspension or tablets. Patients \geq 12 years old assigned to baricitinib will receive tablets. Patients assigned to adalimumab weighing $<$ 30 kg will receive 20 mg, and those \geq 30 kg will receive 40 mg.

Figure JAHW 5.1 Study design for Clinical Protocol I4V-MC-JAHW (d).

Figure JAHW.5.2 illustrates the modified study design for Amendment (e).

Abbreviations: bDMARD = biologic disease modifying antirheumatic drug; IR = inadequate response or intolerance to; MTX = methotrexate; OLE = open label extension.

^a Patients ≥ 6 to <12 years old assigned to baricitinib have the option of receiving the oral suspension or tablets.

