7.5. Evaluation of Immunological Measures

Change from baseline in immunoglobulin levels and peripheral blood immunophenotyping (including T and B cells, T cell subsets, and NK cells) will be evaluated and summarized using descriptive statistics. Patients who are immunized with tetanus-diphtheria-acellular pertussis (TDaP) or pneumococcal conjugate vaccines will have their IgG antibody titers to the antigens evaluated preimmunization and at 4 and 12 weeks postimmunization. A primary immune response will be assessed in patients who have never received TDaP or pneumococcal conjugate vaccines previously, and secondary/booster responses will be assessed if the patients have previously received the vaccines.

8. Safety Analyses

The planned safety analyses are consistent with compound-level standards, which are based on various sources, including company standards, internal and external subject matter experts, and cross-industry initiatives (e.g., white papers produced by a PHUSE Computational Science Working Group [a collaboration with FDA and PHUSE], published in the PHUSE Deliverables Catalog). Descriptions of the safety analyses are provided in this SAP; however, some details are in compound-level safety standards.

For Study JAHW, the following treatment groups and summary for each study period and analysis population are described below in [Table JAHW.8.1](#).

Table JAHW.8.1. Summary of Safety Analysis Population, Baseline and Postbaseline

Population for safety analysis	Part A safety population		Long-term safety population	
	Bari	Ada	Bari	Ada
Treatment period	Part A		Part A+B	
Postbaseline definition	Start with first dose of study treatment, end until treatment period plus up to 30 days off-drug follow-up time	Start with first dose of study treatment, end until treatment period plus up to 30 days off-drug follow-up time.	First day of Bari administration up to data cut for ongoing patients or up to 30 days after the last dose of Bari as long as the patient is in the program.	First day of Ada administration up to data cut for ongoing patients or up to the first dose of Bari or end of study participation as long as the patient is in the program.
Baseline for LLT used in defining treatment-emergence	Screening period up to date of first dose of study treatment.			

Abbreviations: Ada = adalimumab; Bari = baricitinib; LLT = Lowest Level Term.

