8.1. Extent of Exposure

Duration of exposure (in days) to study drug will be summarized for each treatment period with corresponding safety population, which is defined in [Table JAHW.8.1](#).

Total patient years (PY) of exposure will be reported for overall duration of exposure. Descriptive statistics (n, mean, SD, minimum, 1st quartile, median, 3rd quartile and maximum) will be provided for patient-days of exposure, and the frequency of patients falling into different

exposure ranges will be summarized. Exposure ranges will generally be reported in weeks using the following as a general guide:

For Part A safety analysis population (see [Table JAHW.8.1](#))

- ≥ 4 weeks, ≥ 8 weeks, ≥ 16 weeks, ≥ 24 weeks
- >0 to <4 weeks, ≥ 4 weeks to <8 weeks, ≥ 8 weeks to <16 weeks, ≥ 16 weeks to <24 weeks

For long-term safety analysis population (see [Table JAHW.8.1](#)):

- Every 24 weeks or semi-annually

Overall exposure will be summarized in total PY which is calculated according to the following formula:

$$PYE = \text{sum of duration of exposure in days (for all patients in treatment group)} / 365.25$$

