8.5.6. Infections

Infections will be defined using all the PTs from the Medical Dictionary for Regulatory Activities (MedDRA) Infections and Infestations System Organ Class (SOC). The MedDRA terms used to identify infections considered to be opportunistic infections (OIs) are based on Winthrop and colleagues (Winthrop et al. 2015) and are listed in the compound-level safety standards. The list contains narrow (more specific) and broad (less specific) PTs.

The planned summaries are provided in [Table JAHW.8.12.](#) and are described more fully in compound-level safety standards.

Table JAHW.8.12. Summary Tables Related to Infections

Analysis	Population or Analysis Set ^a
The number and percentage of patients with treatment-emergent infections, serious infections, and infections resulting in permanent study drug discontinuation will be summarized using MedDRA PTs.	A, L
The number and percentage of patients with TEAEs of infections by maximum severity will be summarized using MedDRA PTs.	A, L
Listing of patients experiencing TEAE infections will be provided. The listing will include patient demographics, treatment group, treatment start and stop dates, infectious PT event, event start and stop dates, total leukocytes, total lymphocytes, absolute neutrophils, event seriousness, and event outcome	Enrolled
Summary of OIs based on MedDRA PTs	A, L
A summary table of herpes zoster will be provided, including event maximum severity, seriousness, whether resulting in temporary study drug interruption, whether resulting in study drug discontinuation, whether treated with antiviral medication, and event outcome. The incidence rate adjusted for observation time will also be provided.	A, L
The summary table of herpes simplex will include event maximum severity, seriousness, whether resulting in temporary study drug interruption, whether resulting in study drug discontinuation, and whether treated with antiviral medication. The EAIR will also be provided.	A, L
A listing of patients with detectable HBV DNA will be provided	Enrolled

Abbreviations: DNA=deoxyribonucleic acid; EAIR = exposure-adjusted incidence rate; HBV = hepatitis B virus; MedDRA = Medical Dictionary for Regulatory Activities; OI = opportunistic infection; PT = Preferred Term; TEAE = treatment-emergent adverse event.

^a Analysis Sets are abbreviated as follows: A = Part A safety population, L = Long-term.

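### As printed, the long-term adverse-event and infection tables give crude percentages over follow-up running from about 24 to 284 weeks, with exposure-adjusted rates only for herpes zoster and herpes simplex.

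*SAP*

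**What the plan says.** SAP Section 8, Table JAHW.8.1, defines a long-term safety population over Part A+B with a baricitinib and an adalimumab column. The baricitinib window runs to the data cut or to 30 days after the last dose. The adalimumab window is "First day of Ada administration up to data cut for ongoing patients or up to the first dose of Bari", or to the end of study participation.

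Every summary row of Table JAHW.8.2 (SAP 8.2) is a number and percentage of subjects, produced for both the Part A set and the long-term set: the overview, TEAEs by several groupings, severity, SAEs, and discontinuation due to an AE. A typical row reads "The number and percentage of subjects with TEAEs using MedDRA Preferred Term nested within System Organ Class". The only other row is an SAE listing.

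In Table JAHW.8.12 (SAP 8.5.6), infections, serious infections, infections leading to discontinuation, and infections by severity are again number and percentage. The opportunistic-infection row names no measure. For herpes zoster the SAP adds "The incidence rate adjusted for observation time will also be provided", and for herpes simplex an exposure-adjusted incidence rate.

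SAP 8.1 states "Total patient years (PY) of exposure will be reported for overall duration of exposure", and gives long-term exposure in roughly 24-week bands. It does not tie patient-years to the event tables.

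On duration, SAP 4.2 gives "Treatment Period Part A: 24 weeks" and "Treatment Period Part B: 260 weeks". The Protocol synopsis adds "Patients on adalimumab will be discontinued after Week 24". Under the earlier design, adalimumab patients "continued to receive adalimumab for an additional 96 weeks and were then switched to baricitinib for the remaining 164 weeks of Part B" (SAP 5.1).

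**The concern.** A percentage of patients with an event is a risk only when everyone has been watched for about the same time. Here one baricitinib denominator pools patients who leave at Week 24 with patients followed for more than five years, plus ongoing patients counted to whatever the data cut happens to be. The figure will rise with each later cut even if the underlying rate is constant, and it answers no question of the form: how likely is this event within a stated time? This holds for the baricitinib column alone.

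The second problem is the neighbouring column. Adalimumab is now limited to Part A, so in the long-term set it will show lower percentages for most event types because follow-up is shorter. Long-term safety of baricitinib is a stated Part B objective, and these tables are its main summary. The rows that matter most are SAEs, serious infections, discontinuations and individual preferred terms, which are uncommon enough for follow-up time to dominate the percentage.

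**Working it through.** **Durations.** 24 + 260 = 284 weeks, which reproduces the Week 284 end of Part B. 96 + 164 = 260 weeks, which reproduces the length of Part B under the earlier design. An adalimumab patient treated to the switch under that design had 24 + 96 = 120 weeks.

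**Follow-up ratios.**
- Maximum, current design: 284 / 24 = 11.8.
- With off-treatment windows (30 days for baricitinib, 28-day visit for adalimumab): 288.3 / 28 = 10.3.
- Against a 120-week adalimumab patient: 284 / 120 = 2.4.
- If a share s of baricitinib patients reaches Week 284 and the rest stop at Week 24, mean weeks = 284s + 24(1 − s). The documents give no continuation share. I assume s = 40%, 57% and 66.7%, giving 128.0, 172.2 and 197.4 weeks, or ratios to 24 weeks of 5.3, 7.2 and 8.2.

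**Effect on a crude percentage.** With the same constant rate r per patient-year in both arms, the expected percentage with an event is 1 − exp(−rT), where T = weeks × 7 / 365.25. So T = 5.443 years at 284 weeks, 0.460 at 24 weeks and 2.300 at 120 weeks. The documents give no event rate, so r is an assumed range.

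| Assumed rate per 100 PY | 284 weeks | 24 weeks | Ratio, 284 vs 24 | 120 weeks |
|---|---|---|---|---|
| 1 | 5.3% | 0.5% | 11.54 | 2.3% |
| 5 | 23.8% | 2.3% | 10.48 | 10.9% |
| 10 | 42.0% | 4.5% | 9.34 | 20.5% |
| 20 | 66.3% | 8.8% | 7.55 | 36.9% |
| 100 | 99.6% | 36.9% | 2.70 | 90.0% |
| 500 | 100.0% | 90.0% | 1.11 | 100.0% |

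**Mixed continuation, 10 per 100 PY.** The baricitinib percentage is s × 42.0% + (1 − s) × 4.5%. That gives 19.5%, 25.9% and 29.5% for the three shares, against 4.5% at 24 weeks. The same rate thus produces baricitinib figures from 19.5% to 42.0% depending only on how many patients continue.

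**After the change.** Patients with an event divided by time at risk to first event estimates r in each arm, so with equal constant rates the expected ratio is about 1 whatever the follow-up.

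**Precision.** Twenty baricitinib patients followed fully give 20 × 5.443 = 108.9 patient-years. Four adalimumab patients for 24 weeks give 4 × 0.460 = 1.84. At 10 per 100 PY, the chance of no adalimumab event is exp(−0.1 × 1.84) = 83%. With zero events, the exact Poisson 95% upper limit is about 200 per 100 PY.

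**The case against.** **No comparison is planned.** SAP Section 12 says safety analyses focus on baricitinib, with adalimumab described only, and the safety objectives name baricitinib alone. This stands. A reader might infer that the plan is set to report an excess on baricitinib; the documents support only that adjacent columns could be misread. It does not rescue the baricitinib column, which mixes follow-up times on its own.

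**The equal-exposure view already exists.** Every summary row of Table JAHW.8.2 is also produced for Part A, and SAP 8.1 reports patient-years. This stands too. A reader could divide events by total patient-years, though that is not time at risk to first event.

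**Rates may be specified elsewhere.** SAP Sections 8 and 8.2 refer to compound-level safety standards that are not among the documents, and SAP Section 10 gives the DMC incidence rates where applicable. The point is therefore confined to the SAP as printed. But the SAP wrote the rate out for the two herpes rows and not for the others, so the intention is unclear.

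**Twelve-fold overstates the usual case.** Correct. It requires every baricitinib patient to reach Week 284, and by default only responders continue (SAP 5.1).

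**Events of special interest.** A reader might extend the point to VTE and the exposure-adjusted background comparison in Protocol 3.3. The SAP plans no dedicated percentage tables for MACE, VTE, ATE or malignancy; they are listings (SAP 8.5.8 to 8.5.10).

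**The adalimumab rate will be uninformative.** At the minimum of 4 patients this is right. Adjustment removes the bias, not the imprecision.

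**Conclusion.** The point holds for the long-term set in Tables JAHW.8.2 and JAHW.8.12, herpes zoster and simplex excepted. As printed, the baricitinib percentage there has no defined time horizon, and it cannot be read beside adalimumab. The follow-up ratio is 11.8 at most, about 5 to 8 on average under the assumed continuation shares of 40% to 67%, and 2.4 against a 120-week adalimumab patient. Even at 2.4, an assumed 10 per 100 PY gives 42.0% versus 20.5%. The distortion is greatest for uncommon and moderately frequent events and nearly vanishes for rows that almost every patient enters.

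These sizes rest on assumed constant rates and assumed continuation, and on the unseen compound-level standards not already supplying rates. The matter touches no endpoint, decision rule or planned comparison. It is a reporting weakness in the main long-term safety summary, and the SAP already contains the remedy.

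**What to change.** For the long-term set in SAP Tables JAHW.8.2 and JAHW.8.12, add beside number and percentage:
- patients with at least one event per 100 patient-years at risk, with time censored at first event or at the end of the Table JAHW.8.1 window;
- its 95% CI;
- the patient-years.

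Show baricitinib and adalimumab crude percentages side by side for Part A only, where planned exposure is equal. For events reported as listings (MACE, VTE, ATE, malignancy), print total patient-years beside the event count rather than building new rate tables. If the compound-level standards already require such rates, one sentence in SAP 8.2 saying so would be enough.

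The cost is SAP wording and a small amount of programming; patient-years and time-adjusted rates are already in the plan, and no new data are needed. There are two limits. The rate assumes a roughly constant hazard over more than five years, so the exposure bands in SAP 8.1 should be read with it. The adalimumab rate will be very imprecise, and its interval should be shown so that nobody leans on it.
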